1. Klatkiewicz, T., et al., Ultrasonography in the Diagnosis of Temporomandibular Disorders: A Meta-Analysis. Med Sci Monit, 2018. 24: p. 812-817.
2. Su, N., et al., Diagnostic value of ultrasonography for the detection of disc displacements in the temporomandibular joint: a systematic review and meta-analysis. Clin Oral Investig, 2018. 22(7): p. 2599-2614.
3. Melis, M., S. Secci, and C. Ceneviz, Use of ultrasonography for the diagnosis of temporomandibular joint disorders: a review. Am J Dent, 2007. 20(2): p. 73-8.

**PURPOSE OF THE RESEARCH** In the literature, there are not many studies on the diagnostic value of the use of ultrasonography in the diagnosis of temporomandibular joint diseases in dentistry. In this study, it is aimed to contribute to the literature in terms of revealing the reliability of the use of ultrasonography in the diagnosis of temporomandibular joint diseases.

**BENEFITS EXPECTED AT THE END OF THE RESEARCH** By revealing the efficacy and reliability of ultrasonography in the diagnosis of temporomandibular joint diseases, to eliminate the disadvantages of MR and other imaging methods.

**RESEARCH METHOD** Functional joint examination and ultrasonographic examination (USG) will be applied to all volunteers who will participate in the research. In the USG application, when the mouth is open and closed, the right and left joint intervals will be measured and a note will be taken. At the same time, right and left masseter muscle thicknesses will be measured separately at free-closing and tight-closing and a grade will be taken for all groups..

Volunteers to participate in the research will be divided into 4 groups.(I,II,III,IV).For volunteers in group 1 with previously taken MR images, USG and MR findings will be compared. In volunteers in group 2, the values obtained using different probes (linear, hockeystick) will be compared. In the third group of volunteers, the values to be obtained by using the USG probe at different angles (horizontal / longitudinal) will be compared. In volunteers in group 4, the megahertz values of the probe are changed and the findings obtained by examining them separately will be compared.

In addition to evaluating 4 groups separately, at the end of the research, USG data applied to all 4 groups will be

Protocol Information Form for Clinical Research	Doc. Code	Rev. Date/ No:	Page
	Form 3	13.06.2013/ÜDHFKA EK 00	2/6

analyzed by comparing all the findings obtained in functional joint examination.

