## SAMPLE INFORMATION

How was the number of volunteers to participate in the research determined? Explain	When calculating the sample size of our study, reference values in previous similar studies were taken into consideration. When similar dental studies are examined; ( $\mu_1 - \mu_2$ ) and sd values are seen to range from 0.01 to 0.05 (Odacı E. v.d, 2003). When determining the sample size of the study ( $\alpha=0,05$ , $1-\beta=80\%$ ) $f(\alpha, \beta)=7,85$ , $sd =0,05$ and ( $\mu_1 - \mu_2$ ) = 0,02 when taken, it is seen that the sample size is $n = 100$ . It is planned to include 100 volunteers in our research.
Sampling method	Volunteers will be selected from patients who applied to our clinic and who have complaints of temporomandibular joints.

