**WHICH STATISTICAL METHODS WILL BE EVALUATED**

In our study, SPSS application will be used for statistical analysis.

In evaluating the categorical variables, the Chi-Square test will be used to look for a difference between the groups. Normality control of continuous variables will be done with Kolmogorov-Smirnov test.

Difference evaluations of continuous variables between groups will be made with Student's t test in data with normal distribution. Group comparisons for data that are not suitable for normal distribution will be performed with Mann Whitney U test.

Descriptive statistics will be specified by giving mean, standard deviation, minimum and maximum values of all continuous variables. Frequency distributions and percentages of categorical variables will be specified.

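### Groups 2 to 4 compare ultrasound settings without setting, recording or modelling the reading order, so an order effect could be reported as a probe, angle or frequency effect

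*Combined protocol and SAP*

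**What the plan says.** The Research Method section of the combined protocol and SAP gives three of the four groups a comparison of ultrasound settings:

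- Group 2: "the values obtained using different probes (linear, hockeystick) will be compared".
- Group 3: "the values to be obtained by using the USG probe at different angles (horizontal / longitudinal) will be compared".
- Group 4: "the megahertz values of the probe are changed and the findings obtained by examining them separately will be compared". The number of frequency values is not given.

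On recording, the section says that with the mouth open and closed "the right and left joint intervals will be measured and a note will be taken". Masseter thickness is also measured, on both sides, in relaxed and tight closing. On allocation it says only that "Volunteers to participate in the research will be divided into 4 groups", without group sizes.

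Nothing in the available text gives an order for the settings, a way of randomising or balancing it, or an instruction to record it. In the Research Design table, as far as the extracted text can be read, neither a blinding nor a cross-randomisation box is marked.

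The section on statistical methods states: "Difference evaluations of continuous variables between groups will be made with Student's t test in data with normal distribution". The Mann-Whitney U test is the alternative for non-normal data. The section names no paired analysis and no term for order or reading position.

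**The concern.** When two settings are tried on the same person one after the other, the second reading differs from the first in more than the setting. The jaw has been opened and clenched once more, in patients recruited because of joint complaints and pain in the joint and chewing-muscle area. The operator has also had time to settle on landmarks. If one setting always comes first, setting and reading position are the same variable, and the mean difference estimates their sum.

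This affects the technique comparison in three of the four groups. A shift due to position would be published as a difference between probes, angles or frequencies, or could cancel a real one. A larger sample only makes the wrong value more precise. If the order was fixed, the problem cannot be repaired after data collection. If it varied but was not recorded, it cannot be adjusted for.

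**Working it through.** **The plan's own figure.** Sample Information uses f(α, β) = 7.85, SD 0.05 and a difference of 0.02. The two-group formula gives 2 × 7.85 × 0.05² / 0.02² = 98.1, which agrees with the stated 100 as a number per group for two independent groups. The calculation has no bearing on order, but it supplies a scale for the illustration.

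**Bias.** Let D be the true setting difference and b the shift from first to second reading.

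- One order for everyone: expected mean difference = D + b. All of b is bias at any n.
- Two settings, equal numbers in each order: expected mean difference = D + (b − b)/2 = D.
- Two settings, 25 volunteers split 13/12: remaining bias = b × (13 − 12)/25 = 0.04b before any adjustment for position.

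**Inputs for the illustration.** SD 0.05, α 0.05 and the planning difference 0.02 come from Sample Information. The rest are assumptions: 25 volunteers per group (100/4), correlation between readings ρ = 0.5 or 0.8, shift b = 0.01 (half the planning difference) or 0.02, and D = 0.

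**Paired t test, fixed order.** SD of the difference = 0.05 × √(2(1 − ρ)), which is 0.0500 at ρ = 0.5 and 0.0316 at ρ = 0.8. Dividing by √25 gives standard errors of 0.0100 and 0.0063. The non-centrality is b divided by the standard error, with 24 degrees of freedom and critical value 2.064.

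**Independent-sample Student's t, fixed order.** This is the test that the plan names, applied by simulation to the same correlated data. It works with a standard error near 0.05 × √(2/25) = 0.0141, larger than the true 0.0100 or 0.0063, so it rejects too rarely.

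| ρ | Shift b | Bias in mean difference | Non-centrality | False positives, paired t | False positives, independent t |
|---|---|---|---|---|---|
| 0.5 | 0.01 | 0.01 | 1.00 | 16% | about 4% |
| 0.5 | 0.02 | 0.02 | 2.00 | 48% | about 22% |
| 0.8 | 0.01 | 0.01 | 1.58 | 33% | about 1% |
| 0.8 | 0.02 | 0.02 | 3.16 | 86% | about 13% |

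**Larger sample.** With 100 volunteers, b = 0.01 and the paired test, the standard errors halve to 0.0050 and 0.0032. The false-positive rates rise from 16% to 51% (ρ = 0.5) and from 33% to 88% (ρ = 0.8).

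**Balanced order.** A simulation of 40,000 replicates with 24 volunteers, 12 in each order, and the same shifts and correlations gave a bias of about zero. The false-positive rate was 2% to 4.5% without adjustment for position and about 5% with it. A fixed order with the same 24 volunteers gave 15% to 84%.

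**The case against.** The strongest reply is that the plan is silent on order, not wrong about it. A reader might infer that the same setting comes first for everyone and that the operator knows the earlier value when taking the next. The documents say neither. They do not state how many examiners there are, or whether measurements are made live or from stored images. This stands: the confounding is certain only if one order is used throughout. But the plan permits that, and with no record of order nobody could later show that it did not happen.

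Second, the within-volunteer comparison is itself inferred. It is the natural reading, clearest in group 4, but it is never stated, and the named tests are for independent samples. This stands too, so the remedy has to define the pairing as well as the order.

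Third, the large false-positive rates belong to a test that the plan does not name. Under the named test, a shift of 0.01 leaves the rate below 5%. That is correct, but only because the test is too conservative for paired data. The reported mean difference is shifted by the same amount under either test.

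Fourth, the size of any shift is unknown. The planning SD and difference carry no unit and are not tied to joint interval or masseter thickness, so the rates show the mechanism and do not predict a result. A noted earlier value might also pull the next reading towards it and make settings look more alike. The documents give no basis for sizing that, and balancing the order would not remove it.

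Finally, technique comparison is not the only use of these groups. Their ultrasound data are also set against the functional joint examination. The point is therefore limited to the comparisons of settings.

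**Conclusion.** The point holds as a gap in the design that is cheap to close. Reading order is not set, recorded or modelled for the probe, angle and frequency comparisons, and the plan allows one order for all. In that case 100% of any order shift enters the estimated setting difference, whichever test is used and whatever the sample size.

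The documents do not support the stronger conclusions that the order is in fact fixed, that earlier readings are in fact visible, or that false-positive rates of 16% to 86% would follow from the analysis as written. Those rates depend on a paired test, 25 volunteers, the assumed correlations and the assumed shifts. With the named independent-sample test the same inputs give about 1% to 22%. The 4% residual for a 13/12 split applies only to a comparison of two settings, so it carries over to group 4 only if two frequency values are used.

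**What to change.** Add to the Research Method section:

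1. Each volunteer in groups 2, 3 and 4 is examined with every setting being compared in that group.
2. The order of settings is taken from a balanced random list prepared before recruitment. If group 4 uses more than two frequency values, the list is built from a Latin square.
3. The order used is recorded for each volunteer, and each reading is written down before the setting is changed.

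In the statistical methods section, state that settings are compared within volunteer by a paired analysis or a mixed model that includes reading position.

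Hide earlier values from the operator only where this needs no extra staff. Live measurement may require a second recorder or on-screen masking, and the balanced order is worth having without it.

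The cost is a few sentences, a printed list, and occasional changes of probe or setting out of the convenient order. No additional volunteers are needed, nor any scans beyond those that the comparison already implies.

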**REPUBLIC OF TURKEY**  
**ISTANBUL UNIVERSITY INSTITUTE of HALTH SCIENCES**  
**DEPARTMENT OF ORAL AND MAXILLOFACIAL RADIOLOGY**

**RESEARCH PROTOCOL**

**Number of Protocol: 2019/73**

**Date: 09/09/2019**

NAME OF THE RESEARCH	Investigation of the Reliability of Ultrasonography Usage in the Diagnosis of Temporomandibular Joint Diseases: A Prospective Study
-----------------------------	---

RESOURCES OF THE RESEARCH AND RATIONALE	
Today, a significant increase in the prevalence of temporomandibular joint diseases is observed. In addition to the basic clinical examination, there are several methods and techniques for the diagnosis of temporomandibular joint diseases. Magnetic resonance imaging is considered the gold standard in the evaluation of the articular disc as well as soft tissues. Computed tomography is used to diagnose bone lesions such as bone erosion, fractures, postoperative deformities, and deformities of the adjacent temporal bone. All of these methods have limitations. Ultrasound imaging of the joints and surrounding soft tissues is an alternative method for the diagnosis of temporomandibular joint diseases(1). However, the use of ultrasonography in the diagnosis of temporomandibular joint diseases is rare, but although there are several reports suggested in the literature, it is less expensive, less time consuming and easy to apply than other conventional imaging tools such as magnetic resonance imaging, arthrography and computed tomography scanning. recently gained attention and importance in terms of both research and patient care(2,3). The main expectation regarding the use of ultrasound devices in the diagnosis of temporomandibular joint diseases is the use of this method as a screening test. Magnetic resonance imaging, which is associated with exposure to magnetic fields, is very expensive, not found in most medical facilities, and is impossible in patients with claustrophobia. Computed tomography and cone beam computed tomography do not show soft tissues such as joint disc. Computed tomography scans are not performed more than once or twice a year due to exposure to x-rays. Panoramic radiographs available in many dentist clinics show only very advanced changes in the temporomandibular joint. Accurate diagnosis of temporomandibular diseases is not possible only with clinical examination(1).

--	---

Protocol Information Form for Clinical Research	Doc. Code	Rev. Date/ No:	Page
	Form 3	13.06.2013/İÜDHFKA EK 00	1/6

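### The only analysis across all four groups compares USG with the functional joint examination, so it cannot support a conclusion on diagnostic reliability; among the planned comparisons, only group 1 (USG against MR) has a suitable reference

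*Combined protocol and SAP*

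**What the plan says.** PURPOSE OF THE RESEARCH gives the aim as "revealing the reliability of the use of ultrasonography in the diagnosis of temporomandibular joint diseases".

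RESEARCH METHOD sets out the data and comparisons:

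- All volunteers: "Functional joint examination and ultrasonographic examination (USG) will be applied to all volunteers who will participate in the research". MR is not part of this common data set.
- Group 1: "For volunteers in group 1 with previously taken MR images, USG and MR findings will be compared".
- Groups 2 to 4 compare USG with itself under different conditions. For example, "In volunteers in group 2, the values obtained using different probes (linear, hockeystick) will be compared"; group 3 varies the probe angle and group 4 the frequency.
- All four groups: "In addition to evaluating 4 groups separately, at the end of the research, USG data applied to all 4 groups will be" "analyzed by comparing all the findings obtained in functional joint examination" (one sentence, split by a page break).

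RESOURCES OF THE RESEARCH AND RATIONALE says of the two possible comparators:

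- MR: "Magnetic resonance imaging is considered the gold standard in the evaluation of the articular disc as well as soft tissues".
- Clinical examination: "Accurate diagnosis of temporomandibular diseases is not possible only with clinical examination(1").

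The section on statistical methods lists chi-square, Student's t and Mann-Whitney U tests with descriptive statistics. It names no measure of accuracy or agreement and no method for an imperfect reference.

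**The concern.** The aim is diagnostic, so the evidence has to show whether USG findings correspond to true disease. The largest data set, all 100 planned volunteers, is compared only with the functional joint examination. The rationale says that an examination of that kind is not enough alone for an accurate diagnosis, and in the pooled analysis it does stand alone.

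When the two methods disagree, the data cannot say which is wrong. Disease that USG detects and the examination misses looks the same as a USG false positive. Yet finding such disease would be a main reason to use USG as a screening test, which the rationale names as the main expectation for it.

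Group 1 should have USG, MR and functional examination in the same volunteers, but the plan does not set the examination against MR there. The plan also does not say what part the pooled comparison plays in the final conclusion.

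**Working it through.** **The plan's own figure.** The stated sample size is 100, from f = 7.85, sd = 0.05 and a difference of 0.02. Then 2 × 7.85 × (0.05/0.02)² = 98.1, so 100 reproduces as a number per group for comparing two means. It has no link to diagnostic accuracy or agreement, so it lends no support to the pooled analysis as evidence of diagnostic reliability.

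**Which comparison has which reference.**

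| Comparison | Volunteers | External reference |
|---|---|---|
| USG against MR | group 1, size not stated | MR, gold standard for disc and soft tissue |
| Probe, angle, frequency | groups 2, 3, 4 | none (USG against USG) |
| USG against functional examination | all four groups | an examination the protocol does not define |

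**Illustration of the possible size.** The documents give no prevalence or accuracy, so every input here is an assumption: binary results, prevalence p = 0.5, and errors independent given disease status. Let St and Ct be the true sensitivity and specificity of USG, and Sr and Cr those of the examination.

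- Apparent sensitivity = [p·St·Sr + (1−p)(1−Ct)(1−Cr)] / [p·Sr + (1−p)(1−Cr)]
- Apparent specificity = [p(1−Sr)(1−St) + (1−p)·Cr·Ct] / [p(1−Sr) + (1−p)·Cr]

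Perfect USG, examination 80%/70%: sensitivity 0.40/0.55 = 0.727; specificity 0.35/0.45 = 0.778.

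USG 80%/85%, examination 80%/70%: sensitivity (0.32 + 0.0225)/0.55 = 0.623; specificity (0.02 + 0.2975)/0.45 = 0.706.

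| True USG | Examination 80%/70% | Examination 90%/90% |
|---|---|---|
| 100%/100% | 73%/78% | 90%/90% |
| 80%/85% | 62%/71% | 74%/79% |

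**Why more volunteers would not help.** Take methods with equal sensitivity and specificity, at p = 0.5. USG at 0.90 against an examination at 0.80 gives agreement 0.9 × 0.8 + 0.1 × 0.2 = 0.74 and kappa (0.74 − 0.50)/(1 − 0.50) = 0.48. USG at 0.80 against an examination at 0.90 gives the same 0.74 and 0.48. The pooled data would look alike in the two cases, whatever the sample size.

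**Correlated errors.** Take USG 80%/85% and examination 80%/70%. The largest possible positive covariance is 0.80 − 0.64 = 0.16 among the diseased and 0.15 − 0.045 = 0.105 among the non-diseased, 0.265 in sum.

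- Apparent specificity returns to 0.85 when (0.3175 + 0.5c)/0.45 = 0.85, so the summed covariance c is 0.13, about half the maximum.
- Apparent sensitivity returns to 0.80 when (0.3425 + 0.5c)/0.55 = 0.80, so c is 0.195, about three quarters of the maximum.

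Below these levels positive correlation only shrinks the downward bias; above them it reverses the bias.

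**Precision available from group 1.** Its size is not stated. An equal split would give 25 volunteers (assumption). For an observed sensitivity of 0.80, the 95% Wald half-width is 1.96 × √(0.8 × 0.2/n): 0.16 with 25 diseased volunteers, 0.25 with 10, and 0.08 with 100.

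**The case against.** The strongest reply is that the protocol says only that findings will be compared. It does not call the functional examination a reference standard, count disagreement as USG error, or rest its conclusion on the pooled analysis. That analysis comes in addition to the separate group evaluations, one of which is USG against MR, and the Research Design table appears to mark the study as descriptive. Relating joint intervals and masseter thickness to function is a legitimate clinical correlation. All of this stands. A reader might infer that the plan adopts the examination as its diagnostic standard, or that the study has no valid reference; the documents support neither. What remains is that the aim is diagnostic and the plan does not limit what the pooled result may be used for.

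A second reply is that the illustration models an analysis that is not planned. The USG data described are measurements and an undefined grade, with no diagnostic cut-off and no sensitivity or specificity. This also stands: 73%/78% is not a result that this study would report.

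Third, a reader might take the examination as known to be inaccurate. The rationale says only that it is not sufficient alone, and that the functional examination is this clinical examination is a natural inference, not a statement in the protocol.

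Fourth, scoring the examination against MR answers a question that the protocol does not ask, since the aim is the reliability of USG and not its advantage over examination. That is fair. It is still useful because it is the planned comparison that could show what disagreement in the pooled data means.

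**Conclusion.** The concern holds in limited form. The four-group comparison cannot separate USG errors from examination errors, so it cannot support a conclusion on diagnostic reliability. This follows from the design and does not depend on the assumed accuracies.

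The size is unknown. Under the stated assumptions, the shortfall for a perfect USG is 27 and 22 percentage points (sensitivity and specificity) against an examination of 80%/70%, and 10 points on each against one of 90%/90%. It is tempting to conclude that a good USG must look poor, or that any shared error would make it look good. Neither follows: the first depends on how accurate the examination is, and the second needs strong correlation.

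Group 1 keeps a suitable reference in the study, but only for disc and soft-tissue findings, because that is all for which the rationale calls MR the gold standard.

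**What to change.** In RESEARCH METHOD:

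1. State that the diagnostic conclusion, for disc and soft-tissue findings, rests on group 1 USG against MR. Report it with accuracy or agreement measures and confidence intervals, and add these to the statistical methods section. Accuracy measures also need a rule, fixed in advance, for what counts as a positive USG finding, since none is given.
2. In group 1, also score the functional examination against the same MR, so that both methods are judged against one reference in the same joints. Define the functional examination there.
3. Report the four-group comparison of USG with the functional examination as association only, with no claim on accuracy or reliability.

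This needs wording and some added analysis of data already due to be collected, with no extra volunteers or scans. The downside is that the conclusion rests on group 1. It will be less precise than 100 volunteers suggests, and it is limited by the unstated interval between the earlier MR and the USG. The size of group 1 and that interval should therefore be stated and reported. Rewording alone does not make group 1 large enough.
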